#### E. Additional Secondary Investigations

Secondary Endpoints (unpowered) include:

1. AF termination or CL prolongation, as identified by:
  - a. Termination of spontaneous or induced AF by ablation of the source of arrhythmia.
  - b. Reduction of the mean AF rate by at least 10% by ablation of the source of arrhythmia.
2. Single-procedure freedom from AF/AT recurrence from 3-12 months post index ablation procedure (with 90-day blanking period) (Long-Term Effectiveness).
3. Freedom from symptomatic AF/AT recurrence from 3-12 months post index ablation procedure (with 90-day blanking period).
4. Freedom from AF recurrence from 0 – 12 months post index ablation procedure (without 90-day blanking period) (Long-Term Effectiveness).
5. Freedom from AF recurrence at 12 months post index ablation procedure (can include repeat procedures) (Long-Term Effectiveness).

Additional Investigations (unpowered) include:

1. Total RF ablation time.
2. Total Radiation Exposure.
3. Repeat ablation procedure and associated hospitalizations.
4. Quality of Life, as measured by the EQ-5D and AFEQT.
5. Cost-effectiveness analysis.

#### 15.3 POWER AND SAMPLE SIZE ESTIMATION

Since the primary objective of this study relates to the long-term effectiveness of FIRM-guided ablation versus conventional ablation for atrial fibrillation (AF), power and sample size estimates have been calculated relative to that endpoint only. We anticipate enrolling 77 subjects in each treatment arm, plus an additional 8 subjects per arm to account for possible drop-outs / lost to follow-ups, for a total of 170 subjects (in approximately 20 sites).

Description	Assumptions
FIRM Group Freedom from recurrence of AF at 3 months	.55
CONVENTIONAL Group Freedom from recurrence of AF at 3 months	.50
Probability of Type I error ( $\alpha$ ) (two-sided test)	.05
Minimum Total Sample Size (includes 10% adjustment for drop-outs and losses to follow-up)	170 (85 per group)

With 77 subjects in each group, the lower limit of the observed one-sided 95.0% confidence interval will be expected to exceed -0.150 with 80% power when the Standard proportion,  $p_c$ , is 0.500 and the Test expected proportion,  $p_F$ , is 0.550; results are based on 1000 simulations using the Newcombe-Wilson score method to construct the confidence interval. In order to account for potential drop-outs and losses to follow-up, an additional 10% (16) will be added to the total sample size, for a final sample size of 170 (85 per group).

This power and sample size calculation was performed using NQuery 7.0 on the Microsoft Windows 10 operating system.

---

 Newcombe RG (1988) Interval estimation for the difference between independent proportions: comparison of eleven methods. *Statistics in Medicine* 17:873-890.

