### 15.2 STUDY ENDPOINTS

#### A. Long-Term Effectiveness (Primary effectiveness endpoint)

The primary effectiveness endpoint is single-procedure freedom from AF/AT recurrence from 3-12 months after the index AF ablation procedure (with 90-day blanking period).

The hypothesis to be tested is the recurrence rate for FIRM-guided AF ablation is not inferior to that experienced by the conventional AF ablation arm.

The statistical hypothesis for this endpoint is operationalized as follows:

$$H_0: \delta > .15$$

$$H_A: \delta < .15$$

$$\alpha = .05 \text{ (two-tailed)}$$

Where:

$$\delta = p_C - p_F$$

$p_C$  = Proportion free from AF recurrence at twelve (12) months post index ablation procedure for the conventional AF ablation arm (.50)

$p_F$  = Proportion free from AF recurrence at twelve (12) months post index ablation procedure for the FIRM-guided AF ablation arm (.55)

The non-inferiority margin for this hypothesis is 15% (.15). If the lower limit of the two-sided 95% confidence interval calculated for the difference in proportions ( $\delta$ ) is less than .15, the null hypothesis will be rejected and evidence in favor of the alternative (FIRM-guided ablation for atrial fibrillation is not inferior to conventional ablation for atrial fibrillation) affirmed.

This non-inferiority margin was chosen based on that used in the FreezeAF and VGLB trials.

 Luik, Armin MD, et. al. (2010). Rationale and design of the FreezeAF trial: A randomized controlled noninferiority trial comparing isolation of the pulmonary veins with the cryoballoon catheter versus open irrigated radiofrequency ablation in patients with paroxysmal atrial fibrillation. American Heart Journal. 159(4):555-560.

The proportion of successes in each treatment arm shall be estimated using Kaplan-Meier survival estimation.

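### The stated 80% power belongs to a one-sided 95% interval; under the two-sided 95% interval that decides the primary test, 77 per arm gives about 71%

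*Protocol*

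**What the plan says.** Protocol 15.2 A, repeated in SAP 2.2.1, sets the primary non-inferiority test at alpha .05, two-tailed. The margin is given plainly: "The non-inferiority margin for this hypothesis is 15% (.15"). The decision sentence begins "If the lower limit of the two-sided 95% confidence interval calculated for the difference in proportions", so the interval that decides the trial is two-sided 95%.

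Protocol 15.3, repeated in SAP 2.4, sizes the study. Its assumptions table lists alpha .05 and labels it a "two-sided test". The text beneath the table says that, with 77 per group, "the lower limit of the observed one-sided 95.0% confidence interval will be expected to exceed -0.150 with 80% power", assuming success proportions of .50 (conventional) and .55 (FIRM) and 1000 simulations with the Newcombe-Wilson score interval. On numbers it says "We anticipate enrolling 77 subjects in each treatment arm, plus an additional 8 subjects per arm" for losses, making 170 in total.

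Neither document explains why the power statement and the decision rule use different intervals.

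**The concern.** A non-inferiority conclusion depends on one limit of the interval, the one facing the margin. A two-sided 95% interval leaves 2.5% beyond that limit; a one-sided 95% interval leaves 5%. The power statement therefore describes a test with twice the one-sided error rate of the test in the decision rule. Power calculated for the more lenient test overstates the power of the stricter one.

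Two things are at stake. This is the only endpoint for which the study was sized, so the one power figure in the plan would be wrong. The confirmatory significance level is also left open to argument: some results would pass under the interval in the sample size section and fail under the interval in the endpoint section. That has to be settled before outcome data are seen. The quality-of-life and economic analyses are also conditional on meeting the primary endpoints.

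**Working it through.** **Inputs, all from the plan.** Conventional proportion pC = .50, FIRM proportion pF = .55, margin .15, 77 evaluable and 85 randomised per arm, 1:1 allocation, Newcombe-Wilson interval (Protocol 15.3 and SAP 2.4; margin also in Protocol 15.2 A and SAP 2.2.1). Success means that the lower limit for pF − pC exceeds −.15. As in the plan's own calculation, the endpoint is treated as a simple proportion.

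**Step 1: normal approximation.**

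SE = √[(pC(1 − pC) + pF(1 − pF))/n] = √[(.25 + .2475)/77] = .0804

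The distance from the assumed difference to the margin is .05 + .15 = .20, and .20/.0804 = 2.488.

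- One-sided 95% interval (z = 1.645): Φ(2.488 − 1.645) = Φ(.843) = 80.0%.
- Two-sided 95% interval (z = 1.960): Φ(2.488 − 1.960) = Φ(.528) = 70.1%.

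The first line reproduces the plan's 80%.

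**Step 2: exact calculation with the plan's interval.** Build the Newcombe-Wilson limit for every pair of success counts, and add the binomial probabilities of the pairs whose lower limit exceeds −.15.

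| Evaluable per arm | Interval | Newcombe-Wilson, exact | Normal approximation |
|---|---|---|---|
| 77 | one-sided 95% | 80.6% | 80.0% |
| 77 | two-sided 95% | 70.7% | 70.1% |
| 85 | two-sided 95% | 76.8% | 74.4% |

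Exact enumeration of the Wald interval at two-sided 95% gives 70.6% at 77 and 74.1% at 85. The exact figures move in jumps as n changes, because counts are whole numbers, so the spread of 74% to 77% at 85 per arm should be read as a range.

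**Step 3: where 77 comes from.** The standard formula is

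n = (z₁₋α + z₀.₈₀)² × (.25 + .2475)/.20²

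- One-sided .05: (1.645 + .842)² × 12.4375 = 76.9, so 77.
- One-sided .025: (1.960 + .842)² × 12.4375 = 97.6, so 98.

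The plan's 77 is the formula answer at one-sided 5%. The one-sided wording is therefore not a slip in describing a two-sided calculation. With the exact Newcombe-Wilson interval at two-sided 95%, 80% is first reached at 95 per arm (79.1% at 94, 81.8% at 95).

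**Step 4: a result on which the two intervals disagree.** Suppose 38 of 77 succeed in each arm. The Newcombe-Wilson lower limit for pF − pC is −.130 with the one-sided 95% interval and −.154 with the two-sided 95% interval. Identical observed rates would pass the first and fail the second.

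**The case against.** There are four points on the other side.

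First, a one-sided 5% test may be what the sponsor meant. If so, the decision rules and the assumptions tables in both documents are wrong instead. The weight of the text favours the two-sided interval, and some correction is needed either way.

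Second, the planned analysis estimates the proportions by Kaplan-Meier, with censoring (SAP 2.5), and neither document names the interval method for it. This stands as a caveat: 70.7% is the power of the plan's own binary calculation at the correct level, not of the Kaplan-Meier comparison. Using Kaplan-Meier does not turn a 2.5% limit into a 5% one, so it does not rescue the stated figure.

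Third, the decision rule has a separate fault. It defines the difference as pC − pF and then asks whether the lower limit is below .15, which is met almost always if read literally. The figures here assume the evident intent, that the limit facing the margin must clear it. This agrees with the −0.150 criterion in Protocol 15.3.

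Fourth, the mismatch does not raise the risk of a false non-inferiority claim if the two-sided rule is applied. At pC = .50, pF = .35 and 77 per arm, the exact rejection probability is about 2.6%. That is correct: the harm is lost power and an ambiguous success criterion, not inflated type I error.

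**Conclusion.** The concern holds. The plan's 80% is reproducible only at one-sided 5%, which is not the level of the primary test. On the sponsor's own assumptions, the two-sided 95% interval has about 71% power at the planned 77 evaluable per arm, so the chance of failing to show non-inferiority is about 29% rather than 20%. If no subject were lost, 85 per arm would give about 74% to 77%, still short of 80%. These figures rest on the plan's rates and margin, on its treatment of the endpoint as a simple proportion, and on the margin-side reading of the decision rule.

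**What to change.** In Protocol 15.3 and SAP 2.4, delete the one-sided 95.0% wording and state the power for the two-sided 95% interval: about 71% with 77 evaluable per arm, and about 77% (exact Newcombe-Wilson) if all 85 are evaluable. One significance level then applies throughout. This is a text correction in two documents. It needs no extra patients; its cost is a less favourable stated power.

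If the sponsor wants to keep 80% power, the study has to be re-sized to 95 (exact) or 98 (formula) evaluable per arm. Allowing for 10% loss, 95/.9 = 106 and 98/.9 = 109 per arm, so 212 to 218 in total against the present 170.

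The other consistent route is to declare a one-sided 5% test everywhere, including Protocol 15.2 A, SAP 2.2.1 and both assumptions tables. That loosens the primary test to fit the calculation, so it would need an explicit justification written before outcome data are seen.

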## 16 PUBLICATION POLICY

The data generated in this clinical study are the property of the Sponsor and are confidential. As the study Sponsor, Abbott retains the first right to disclose the results of the Study through a publication such as the ICMJE or any other public disclosure 12 months after the close-out of the last study center. A Publication Steering Committee (PSC) may be formulated to oversee the publication process. The PSC may include Principal Investigator(s), members of the Steering Committee, investigators and other individuals who have expertise in the area and employees of Abbott. All manuscripts and abstracts will be reviewed and approved by the PSC and/or Abbott. Authorship on the primary publication of the results from this study will be based on contributions to study design, enrollment, data analysis, and interpretation of results.

## 1 INTRODUCTION

### 1.1 Study Overview

#### 1.1.1 Title

FIRMAP AF is a prospective randomized study to assess the safety and effectiveness of FIRM-guided ablation versus conventional pulmonary vein isolation (PVI) ablation for the treatment of paroxysmal atrial fibrillation (AF) for subjects without prior AF catheter ablation.

#### 1.1.2 Objectives

The primary objective is to compare the safety and effectiveness of FIRM-guided ablation procedures with conventional ablation for the treatment of paroxysmal atrial fibrillation (AF) for subjects without prior AF catheter ablation.

The secondary objective is to evaluate the treatment time and quality of life outcomes.

#### 1.1.3 Patient Population

FIRMAP AF will include subjects experiencing at least two (2) documented episodes of paroxysmal atrial fibrillation during the three (3) months preceding study entry with clinical indication for AF ablation per guidelines. At least one episode should be documented by rhythm strip or ECG.

#### 1.1.4 Inclusion Criteria

- Male or female 18 – 80 years of age.
- Experiencing at least two (2) documented episodes of **paroxysmal** atrial fibrillation in the last 3 months preceding study entry with clinical indication for AF ablation per guidelines. At least one episode should be documented by rhythm strip or ECG.
- Indicated for AF ablation according to current EHRA guidelines.
- Prescribed with oral anticoagulation therapy, in indicated patients per the latest EHRA guidelines.
- Willingness and able to remain on anti-coagulation therapy as per the latest EHRA guidelines.
- Left atrial diameter < 5.5 cm as measured and image ((CT/TEE/TTE/ MRI or ICE) documented within previous six months up to pre-procedure.
- Sustained AF (>5 min uninterrupted) during the electrophysiology procedure. If the subject is not experiencing spontaneous, sustained AF, it may be induced by burst pacing (typically from the coronary sinus) with or without isoproterenol infusion in conventional clinical fashion.
- Willingness, ability and commitment to participate in baseline and follow-up evaluations.
- Signed patient informed consent form.

### 1.1.5 Exclusion Criteria

- Presence of structural heart disease of clinical significance including:
  - Coronary artery disease with either:
    - Coronary artery bypass surgery (CABG) within the last 180 days (six months), or
    - Stable/unstable angina or ongoing myocardial ischemia.
  - Congenital heart disease where either the underlying abnormality or its correction prohibits or increases the risk of ablation.
- NYHA Class III – IV.
- Ejection fraction < 40% (within previous six months).
- History of myocardial infarction (MI) within the past three months.
- Any concomitant arrhythmia or therapy that could interfere with the interpretation of the results from this study.
- ASD closure device, LAA closure device, prosthetic mitral or tricuspid valve, or permanent pacemaker.
- Any previous AF catheter ablation.
- History of prior cardioversion for AF lasting > 48 hours.
- Continuous AF episode lasting > 7 days immediately prior to the procedure without a sinus rhythm.
- Severe electrolyte abnormalities at time of the ablation procedure or atrial fibrillation secondary to electrolyte imbalance, thyroid disease, or reversible non-cardiac cause.
- Atrial fibrillation from a reversible cause (e.g., surgery, hyperthyroidism, pericarditis).
- Contraindication to Heparin and Warfarin/other novel oral anticoagulants (e.g. dabigatran, rivaroxaban, apixaban).
- History of pulmonary embolus within one year of enrollment.
- Acute pulmonary edema.
- Atrial clot/thrombus on imaging such as on a trans-esophageal echocardiogram (TEE) performed within 72 hours of the procedure if deemed appropriate by investigator.
- History of a cerebrovascular disease (including stroke or TIA) within the last 12 months.
- Any anticipation of cardiac transplantation or other cardiac surgery within the next 12 months.
- History of thromboembolic event within the past 3 months.
- Diagnosed atrial myxoma.
- Significant pulmonary disease, (e.g. restrictive pulmonary disease, constrictive or chronic obstructive pulmonary disease) or any other disease or malfunction of the lungs or respiratory system that produces severe chronic symptoms and significantly increases risk to sedation or anesthesia.
- Acute illness or active systemic infection or sepsis.
- History of blood clotting abnormalities or bleeding abnormalities.
- Life expectancy of less than 12 months.
- Presence of intramural thrombus, tumor, or other abnormality that precludes catheter introduction or safe manipulation.

	FIRMAP AF Statistical Analysis Plan		Rev: 01	Effective: 05JAN2016
---	-------------------------------------	--	---------	-------------------------

- Women who are pregnant.

### 1.1.6 Study Masking

FIRMAP AF is a multi-center, open-label, randomized study (no masking).

### 1.1.7 Randomization

Block randomization stratified by center will be used to assign subjects (1:1) to the conventional AF ablation treatment with PVI (PVI group), or to the FIRM-guided AF ablation procedure without PVI (FIRM group).

## 1.2 Study Outcomes

### 1.2.1 Primary Outcomes

#### 1.2.1.1 Acute Safety

Freedom from procedure-related serious adverse events within 7 days of the procedure.

#### 1.2.1.2 Long Term Safety

Freedom from procedure-related serious adverse events within one year of the index procedure.

#### 1.2.1.3 Acute Effectiveness (secondary endpoint only)

FIRM group: Elimination of identified AF rotors

Control group: Isolation of all pulmonary veins

#### 1.2.1.4 Long Term Effectiveness (primary effectiveness endpoints)

Single-procedure freedom from AF recurrence from 3-12 months after the index AF ablation procedure (with 90-day blanking period).

\*Freedom from AF recurrence is defined as no documented episodes of AF > 30 seconds with conventional non-invasive monitoring. In the case of a cardiac implanted electronic device (CIED), freedom from AF recurrence is defined as no documented episodes of AF > 30 seconds in a 72-hour window at the follow-up visits in addition to any symptomatic episodes with documented AF > 30 seconds.

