**Table 1 – Primary Effectiveness Endpoint**

Endpoint	Definition
Long term success	
Single-procedure freedom from AF/AT recurrence from 3-12 months post index ablation procedure (with 90-day blanking period).
 
* Freedom from AF/AT recurrence is defined as no documented episodes of AF/AT > 30 seconds with conventional non-invasive monitoring. In the case of a cardiac implanted electronic device (CIED), freedom from AF recurrence is defined as no documented episodes of AF/AT > 30 seconds in a 72-hour window at the follow-up visits in addition to any symptomatic episodes with documented AF > 30 seconds. AT recurrence does not include episodes of CTI (cavotricuspid isthmus) dependent flutter.

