#### ***1.2.1.5.2 Long-Term Effectiveness***

1. Single-procedure freedom from AF/AT recurrence from 3-12 months post index ablation procedure (with 90-day blanking period).
2. Freedom from symptomatic AF/AT recurrence from 3-12 months post index ablation procedure (with 90-day blanking period).
3. Freedom from AF recurrence from 0-12 months post index ablation procedure (without 90-day blanking period).
4. Freedom from AF recurrence at 12 months post index ablation procedure (can include repeat procedures).

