### 2.2 Study Endpoints

#### 2.2.1 Long-Term Effectiveness (Primary effectiveness endpoint)

The primary effectiveness endpoint is single-procedure freedom from AF/AT recurrence from 3-12 months after the index AF ablation procedure (with 90-day blanking period)..

The hypothesis to be tested is the recurrence rate for FIRM-guided AF ablation is not inferior to that experienced by the conventional AF ablation arm.

The statistical hypothesis for this endpoint is operationalized as follows:

$$H_0: \Delta > .15$$

$$H_A: \Delta < .15$$

$$\alpha = .05 \text{ (two-tailed)}$$

Where:

$$\Delta = p_C - p_F$$

$p_C$  = Proportion free from AF recurrence at twelve (12) months post index ablation procedure for the conventional AF ablation arm (.50)

$p_F$  = Proportion free from AF recurrence at twelve (12) months post index ablation procedure for the FIRM-guided AF ablation arm (.55)

The non-inferiority margin for this hypothesis is 15% (.15). If the lower limit of the two-sided 95% confidence interval calculated for the difference in proportions ( $\Delta$ ) is less than .15, the null hypothesis will be rejected and evidence in favor of the alternative (FIRM-guided ablation for atrial fibrillation is not inferior to conventional ablation for atrial fibrillation) affirmed.

This non-inferiority margin was chosen based on that used in the FreezeAF and VGLB trials.

 Luik, Armin MD, et. al. (2010). Rationale and design of the FreezeAF trial: A randomized controlled noninferiority trial comparing isolation of the pulmonary veins with the cryoballoon catheter versus open irrigated radiofrequency ablation in patients with paroxysmal atrial fibrillation. American Heart Journal. 159(4):555-560.

The proportion of successes in each treatment arm shall be estimated using Kaplan-Meier survival estimation.

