#### 2.3 Additional Secondary Investigations

Secondary Endpoints (unpowered) include:

1. AF termination or CL prolongation, as identified by:

- a. Termination of spontaneous or induced AF by ablation of the source of arrhythmia.
- b. Reduction of the mean AF rate by at least 10% by ablation of the source of arrhythmia.
- 2. Single-procedure freedom from AF recurrence from 3-12 months post index ablation procedure (with 90-day blanking period) (Long-Term Effectiveness).
- 3. Freedom from symptomatic AF/AT recurrence from 3-12 months post index ablation procedure (with 90-day blanking period).
- 4. Freedom from AF recurrence from 0 – 12 months post index ablation procedure (without 90-day blanking period) (Long-Term Effectiveness).
- 5. Freedom from AF recurrence at 12 months post index ablation procedure (can include repeat procedures) (Long-Term Effectiveness).

Additional Investigations (unpowered) include:

- 1. Total RF ablation time.
- 2. Total Radiation Exposure.
- 3. Repeat ablation procedure and associated hospitalizations.
- 4. Quality of Life, as measured by the EQ-5D and AFEQT.
- 5. Cost-effectiveness analysis.

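### The SAP names two different primary endpoints (AF-only in 1.2.1.4, AF/AT in 2.2.1) and swaps each with the secondary, so the non-inferiority verdict can depend on the section followed

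*SAP*

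**What the plan says.** The SAP describes the primary endpoint twice, in current text, and the two descriptions differ.

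- **SAP 1.2.1.4**, under a heading that labels it primary: "Single-procedure freedom from AF recurrence from 3-12 months after the index AF ablation procedure (with 90-day blanking period"). Its event definition is "Freedom from AF recurrence is defined as no documented episodes of AF > 30 seconds with conventional non-invasive monitoring". Atrial tachycardia (AT) is not mentioned.
- **SAP 1.2.1.5.2, item 1**, secondary: "Single-procedure freedom from AF/AT recurrence from 3-12 months post index ablation procedure (with 90-day blanking period").
- **SAP 2.2.1**, the section with the hypothesis and decision rule: "The primary effectiveness endpoint is single-procedure freedom from AF/AT recurrence from 3-12 months after the index AF ablation procedure".
- **SAP 2.3, item 2**, unpowered secondary: "Single-procedure freedom from AF recurrence from 3-12 months post index ablation procedure (with 90-day blanking period").

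So AF-only and AF/AT trade places between the outcomes section and the methods section. SAP 2.2.1 is also mixed internally, because the control-arm parameter is "Proportion free from AF recurrence at twelve (12) months post index ablation procedure for the conventional AF ablation arm (.50") and the FIRM parameter has the same form. Protocol 15.2 A repeats this.

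Protocol Table 1 is on the AF/AT side: "Freedom from AF/AT recurrence is defined as no documented episodes of AF/AT" longer than 30 seconds, with CTI-dependent flutter not counted. The SAP does not carry that flutter rule. Protocol Table 2 and 15.2 E list the AF/AT endpoint again as item 2 of the unpowered secondaries, so the protocol duplicates its primary and has no AF-only endpoint for months 3-12.

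**The concern.** A confirmatory non-inferiority claim needs one prespecified endpoint. Here a patient whose only recurrence is AT fails under SAP 2.2.1 and succeeds under SAP 1.2.1.4. The SAP's only event definition is the AF-only one, so a programmer working from 2.2.1 finds neither an AT event definition nor a flutter rule there.

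Three things are at stake. The verdict may differ between the two readings of the same data. If the definition is settled with data in hand, the false-positive rate exceeds that of either endpoint alone. And one arm receives pulmonary vein isolation while the other receives rotor ablation without it, so equal AT-only recurrence in the two arms cannot be presumed. If it differs, the two definitions estimate different treatment differences.

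**Working it through.** **Inputs from the documents.** Margin .15; planning rates pC = .50 and pF = .55; 77 per arm before and 85 after the dropout addition; Newcombe-Wilson interval (SAP 2.2.1 and 2.4). **Assumption.** The AT-only recurrence rate is not given, so a range is used.

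**Interval.** For each arm the Wilson limits (l, u) at n are
(p + z²/2n ± z·√[p(1−p)/n + z²/4n²]) / (1 + z²/n).
The lower limit for FIRM minus control is
L = (pF − pC) − √[(pF − lF)² + (uC − pC)²].
Non-inferiority is declared if L > −.15. This is the same as requiring the upper limit for pC − pF to be below .15. SAP 2.2.1 refers to the lower limit for pC − pF, which is a separate matter. The form used here matches the sizing statement in SAP 2.4.

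**The plan's own figure.** With 77 per arm and a one-sided 95% limit, exact enumeration over two binomial arms gives power .806. The stated 77 and 80% reproduce. With a two-sided 95% interval, as in SAP 2.2.1, power is .707 at 77 per arm and .768 at 85.

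**One patient can decide the result** (85 per arm, two-sided 95%).

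- AF-only freedom 43 vs 43: p = .5059, Wilson limits .4017 and .6096 in each arm. L = 0 − √(.1042² + .1037²) = −.147. Non-inferior.
- One FIRM patient has AT only, so AF/AT freedom is 42 vs 43: pF = .4941, lF = .3904. L = −.0118 − √(.1037² + .1037²) = −.158. Not shown.

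**How often the verdicts differ.** Each patient is drawn as free of both, AT only, or AF, and the rule is applied to both endpoints in the same patients. With equal AT-only rates in the arms, the true difference is the same under both definitions. The null case uses .50 vs .35, which sits at the margin for both.

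| AT-only rate, each arm | Opposite verdicts at .50/.55 | Type I error, favourable definition taken |
|---|---|---|
| 1-3% | about 4-8% | about 3.2-3.7% |
| 5% | about 10.5% | about 3.8-4.0% |
| 10% | about 15% | about 4.3-4.4% |

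With one endpoint fixed in advance, the type I error is about 2.8%.

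**If AT-only recurrence differs between arms by 5 points.** The difference pC − pF moves by .05, which is .05/.15 = one third of the margin. Exact power at 85 per arm is 76.8% at −.05, 53.1% at 0 (more AT in FIRM) and 91.8% at −.10 (more AT in control). At 77 per arm the figures are 71%, 47% and 88%.

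**Effect on the sizing itself.** If .50 and .55 are AF-only rates and AT-only recurrence is 5% in both arms, AF/AT freedom is .45 and .50 and power at 77 per arm, one-sided .05, is still .806. The sizing suffers only if the arms differ.

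**The case against.** The strongest reply is that the intended endpoint is not in real doubt. Protocol Table 1, Protocol 15.2 A and SAP 2.2.1 all name AF/AT, and SAP 2.3 is consistent with them. The outlier is the SAP's outcomes list, which looks like text that was not updated. This is a good reason to reconcile towards AF/AT. It does not remove the conflict: the SAP (effective 5 January 2016) postdates Protocol Amendment 1 (15 December 2015), neither document states precedence, and the outlying section holds the SAP's only event definition.

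Some side points are weaker. Table 1 itself uses AF recurrence as shorthand for AF/AT in patients with an implanted device, so the pC and pF wording need not mean AF-only. An AF-only definition needs no flutter exclusion, so that omission matters only once AF/AT is adopted. The duplicated protocol secondary cannot alter the primary verdict.

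On size, it is fair that the percentages rest on assumed AT-only rates, that 85 evaluable per arm leaves no dropout, that simple proportions stand in for the planned Kaplan-Meier estimates, and that even 4.4% is below the one-sided 5% used for sizing. These points change the magnitude. They do not make the endpoint unique.

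**Conclusion.** The point holds: the SAP is wrong as written, because its primary endpoint is not uniquely defined and the two candidates swap roles with the secondary. That conclusion rests on the text alone.

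The numerical consequence is conditional. For AT-only rates of 5-10% in both arms, roughly one trial in nine to one in seven would reach opposite verdicts, and free choice of definition would raise the type I error by about 1 to 1.6 percentage points. The effect shrinks at lower rates and vanishes if no patient has AT alone. It is larger if the arms differ: with assumed AT-only rates of 3% in control and 8% in FIRM, at 77 per arm and two-sided 95%, verdicts disagree in 25% of trials. This must be corrected, because it concerns the trial's only powered test.

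**What to change.** 1. Rewrite SAP 1.2.1.4 to match Protocol Table 1: AF/AT longer than 30 seconds, CTI-dependent flutter excluded, from the end of the 90-day blanking period to month 12. Put the full event definition in SAP 2.2.1 or refer to it there.
2. Make AF-only freedom over months 3-12 the secondary in SAP 1.2.1.5.2 item 1, as SAP 2.3 already does. Use it to replace the duplicated primary in Protocol Table 2 and 15.2 E, item 2.
3. Reword pC and pF in SAP 2.2.1 and Protocol 15.2 A as freedom from AF/AT recurrence. In the sizing tables (SAP 2.4, Protocol 15.3), correct the endpoint label and the 3-month time label, and state which endpoint the .50 and .55 refer to.
4. Repair the implanted-device clause in Table 1 before copying it. Its 72-hour window counts AF/AT, but its symptomatic-episode part counts documented AF only.
5. State which document prevails if the SAP and protocol differ.

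The SAP changes are wording only and should be dated before database lock. The protocol changes are also wording, but under Protocol 12.1 an amended protocol needs ethics committee or competent authority approval. No change in sample size or data collection follows from this point.
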